11.5 Reporting of Adverse Events

All AEs must be recorded in the eCRF, defining relationship to study medication, intensity, seriousness, action taken with study drug, and outcome. AEs should also be recorded by the investigator in the patient file/notes.

11.6 Timelines and Reporting of SAE

All SAEs must be reported, whether or not considered attributable to the study drug on a separate SAE Report Form. SAEs will be reported from signing of informed consent.

████████████████████ will be responsible for reporting all SAEs in accordance with International Council for Harmonisation of Technical Requirements for Pharmaceuticals for Human Use (ICH) Good Clinical Practice (GCP) and local regulations. The sponsor and ██████████ will complete and sign a "Pharmacovigilance Working Agreement" agreement covering the safety reporting responsibilities in the

study. This agreement will ensure the sponsor is directly informed of each SAE reported by the investigators.

In order to meet the specified reporting requirements investigators should adhere to the following process for recording and reporting SAEs.

It is the investigator's responsibility to, as soon as he/she is aware of a potential SAE, he/she should contact [REDACTED] by fax or e-mail, and in any case no later than 24 hours after the knowledge of such a case.

At the time of initial reporting, the investigator must provide as a minimum requirement, the patient number, birth date, nature of the SAE, and a preliminary assessment of causality. The investigator should follow-up the initial notification of the potential SAE by faxing or e-mailing a copy of the SAE reporting form to [REDACTED] at the numbers/e-mail address provided in the investigator Site File and on the SAE Report Form. The faxed/e-mailed SAE Reporting Form should be received by [REDACTED] within 24 hours of the initial notification of the event.

It is the investigator's responsibility to report to [REDACTED] follow-up information on an existing SAE that is fatal or life-threatening within 5 days after the initial report. Where appropriate, hospitalization or autopsy reports should be made available. All SAEs will be followed up until resolution (i.e., asymptomatic, stabilization or death).

It is [REDACTED] responsibility to receive e-mail or fax copies of the SAE report form and other relevant eCRF pages from the investigators. The Drug Safety unit at [REDACTED] will review the information provided on the form and enter it into the safety data base. The SAE report will be assigned a unique number that will be entered on the SAE Report Form, and will be used to identify the report in all future communication. A notification of receipt of the report will be sent to the reporter, either by fax or e-mail within 48 hours. [REDACTED] will contact the investigator directly if there is any inconsistencies and missing information.

[REDACTED] is responsible for the timely submission of SUSARs to the Competent Authorities and IECs according to appropriate Competent Authority and IEC requirements. It is [REDACTED]'s responsibility to report SUSARs to investigators according to ICH GCP and to local regulations. Competent Authorities will be notified of all SUSARs through the EudraVigilance database.

Fatal and life-threatening SUSARs should be reported by [REDACTED] as soon as possible to the Competent Authorities and Ethical Committees, and in any case no later than seven (7) calendar days, after knowledge by the Sponsor/[REDACTED] of such a case. Relevant follow-up information on the case will be subsequently communicated within an additional eight (8) days. All other SUSARs shall be reported to the Competent Authorities concerned and to the Ethics Committee concerned as soon as possible but within a maximum of fifteen (15) days of first knowledge by [REDACTED]

11.7 Unresolved Events

If an AE/SAE is present when the patient has completed the study the course of the event must be followed until final outcome is known or the condition is stable.

11.8 Pregnancy Report Form

Pregnant and lactating women will not be included in the study. Menarchal females must have a negative urine pregnancy test prior to randomization and a negative urine pregnancy test at each study visit with Diamyd/Placebo administration, prior to injection of study drug. Patients will be required to use an adequate form of birth control during the study. At Visit 2 the need for birth control will be re-assessed. Patients and their partners will be strongly advised to avoid pregnancy for 1 year following the last dose of Diamyd/Placebo and instructed to use adequate birth control.

A pregnancy occurring during the trial must be recorded on the Pregnancy Report Form and no further drug doses will be given. If the pregnancy is verified prior to any of the injections, no further injection shall be given.

The Pregnancy Report Form should be faxed or e-mailed within 24 hours of awareness to [REDACTED]. A copy of the report should be filed at the study site for follow-up until delivery. Any pregnancy must be followed until delivery or to the end of pregnancy.

11.9 Direct Access to Source Data/Documents

The sponsor should ensure that it is specified in the protocol or other written agreement that the investigator(s)/institution(s) will permit trial-related monitoring, audits, IEC review, and regulatory inspection(s), providing direct access to source data/documents.

12 DATA HANDLING

12.1 Data Management

Data management and handling of data will be conducted according to the study specific Data Management Plan with ICH guidelines and [REDACTED] standard operating procedures (SOPs).

An eCRF system will be used to capture data from the study. Data entry will be performed by the study site personnel. Validation and data queries will be handled by the [REDACTED] Data Management Team. The data will be subjected to validation according to [REDACTED] SOPs in order to ensure accuracy in the collected eCRF data.

Changes to the data in the eCRF will be made at the site by the study site personnel. The eCRF will have an audit trail with appropriate functionality for data capture, tracking and documentation of any queries or changes. Electronic signatures will be used to lock the data and identify the person entering or changing the data. Before database closure a reconciliation will be performed between the SAEs entered in the safety database and the study database. After database closure, the database will be exported as SAS[®] data sets.

Any deviations, i.e. discrepancies and additions from the process defined in the Data Management Plan, will be described in a study specific Data Management Report.

13 STATISTICAL METHODS

13.1 Estimation of Sample Size

A total sample size of 106 patients is planned for a 1:1 randomization in order to provide 90% power to detect a 50% difference in geometric mean C-peptide ($AUC_{\text{mean } 0-120 \text{ min}}$) during an MMTT at 15 months between the active arm and placebo arm using a two-sided test at the 0.05 significance level. The sample size has been adjusted to allow for 10% loss to follow-up. This is based upon a t-test employing $\ln(X+1)$ normalizing transformation of C-peptide ($AUC_{\text{mean } 0-120 \text{ min}}$) during an MMTT at 15 months and assumed mean and standard deviation estimates, on the transformed scale, of 0.134 and 0.20, respectively¹

It is estimated that there will be a screening failure rate of 16%. To ensure that 106 patients are screened and enrolled approximately 127 patients will be screened.

13.2 Statistical Analyses

A detailed statistical analysis plan (SAP) will be written and finalized well in advance of database lock. The plan will follow the outline of the statistical analyses presented below, but details necessary to complete the statistical analyses will be given.

13.2.1 Data Sets to be Analyzed

The following analysis sets will be used for the statistical analysis and presentation of data:

- The **screened set** will consist of all patients that were screened for participation in this study
- The **randomized set** will consist of all patients that were randomized.
- The **Safety Set** will consist of all randomized patients who received at least one injection.
- The **Full Analysis Set (FAS)** will consist of all randomized patients who have received at least one dose of study medication and have at least one post-baseline assessment and corresponding baseline measurement of any efficacy variable.
- The **Extension set** will consist of the subset of the FAS that participated in the Extension Study Period.
- The **Completers Set** will consist of all patients in the FAS who have completed the main study period and who have primary efficacy data available at Visit 7.
- The **Per Protocol Set (PPS)** will consist of all patients in the FAS who received all three study drug injections, and do not have any other major

¹ Lachin et.al Sample Size Requirements for Studies of Treatment Effects on Beta-Cell Function in Newly Diagnosed Type 1 Diabetes, 2011, 6(11):e26471

protocol violations which will affect the assessment of efficacy. Major protocol violations include:

- Missed at least one scheduled injection of IMP
- C-peptide samples received by lab later than 48 hours after sampling

The final criteria for PPS, regarding which protocol deviations that warrant exclusions, will be determined when all data on protocol violations/deviations are available and before breaking the blind. The final criteria will be documented in the SAP or in the Pre-Analysis Review form issued by the statistician prior to unblinding of the data.

The Screened set will be used for presentation of study disposition of patients.

The FAS is considered as the primary analysis dataset, and will be used for all primary, secondary and exploratory efficacy endpoints. The primary efficacy analyses will be repeated using the PPS and the completers set and these analyses will be regarded as sensitivity analyses. Any discrepancy between the results from the FAS and the PPS or the completers set will be analyzed and discussed in the Clinical Study Report.

The secondary variables will be analyzed based on FAS only.

The analysis datasets will be applied at the main study analyses as well as the whole study period.

Baseline presentations will be based on the safety set and on the FAS. Safety presentations will be based on the safety set. FAS will be analysed according to randomised (planned) treatment. Safety and PPS will be analysed on actual treatment received.

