8.5 Patient Withdrawal

In accordance with the Declaration of Helsinki, the investigator must explain to the patient that they have the right to withdraw from the study at any time, and that this will in no way prejudice their future treatment. The reason for any kind of withdrawal must be recorded on the appropriate section of the eCRF.

There will be two main categories for withdrawals from the study:

Complete withdrawal (i.e. stopping investigational product(s) and also continued efficacy and safety evaluations). In order to achieve as complete as possible 15 month follow-up, whenever feasible, patients that are considered for complete withdrawal should be asked if they could consider to return for a 15-month visit, preferable complete visit but as a minimum do the MMTT, C-peptide and HbA1c sampling, and collection of AEs. Attempts should be made to contact patients lost to follow-up with respect to this.

Standard reasons for withdrawing from further participation in the study and from the follow-up visits may be:

- Patient's decision (withdrawal of consent to participate)
- Patient lost to follow-up

Withdrawals from investigational product(s) (i.e. stopping one or several investigational products, but continuing follow-up visits, including efficacy and safety evaluations)

Standard reasons from withdrawing from taking further investigational product, but continuing follow-up visits and safety evaluations may be:

- Unacceptable AEs
- Patient request
- Investigator's discretion
- Patient lost to follow-up/non-attendance
- Intercurrent illness
- The patient becomes pregnant

Diamyd/placebo should not be given to the patient if the patient after inclusion in the study develops/experiences:

- Brain damage, epilepsy, head trauma, neurological disease
- Any active, serious hormonal disease other than T1D
- Other severe autoimmune disease (except celiac disease which is accepted for inclusion)
- Immune-suppressive treatment
- Cancer, cancer treatment
- Any other diabetes drugs other than insulin (and the combination regimen administered in this study)
- Any vaccination

- Drug/alcohol abuse
- Becomes pregnant or is no longer willing to use safe contraceptives during the study

Vitamin D/placebo treatment should not be continued if the patient after inclusion in the study develops/experiences:

- Symptoms of hypercalcemia such as tiredness, euphoria, drowsiness, nausea, weight loss, thirst, polyuria, nefrocalcinosis, renal failure
- Arrhythmia

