9.2.1 Adverse Events

AEs will be recorded throughout the study period from Visit 2 (baseline) to completion of Visit 8. Events occurring until the day before first administration of investigational medicinal product (IMP) (Visit 2) will be recorded as medical history and as AEs from start of first administration of IMP (day of Visit 2 and onwards).

SAE will be recorded from signing ICF.

AEs will be coded using the current version of Medical Dictionary for Regulatory Activities (MedDRA).

For further information of definitions and reporting of AEs and SAEs and Incidents, see Section 11.

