10 TREATMENT OF PATIENTS

10.1 Study Treatment

Study medication: Diamyd® intralymphatic injection

Diamyd/placebo will be injected directly into the inguinal lymph node at Visits 3, 4 and 5 (Days 30, 60 and 90). The Diamyd/placebo injection directly into the inguinal lymph node need to be done by an appropriately qualified person at the X-ray department by help of ultrasound technique. All possible efforts should be made to use the same lymph node for all 3 injections. For more information regarding the injection please refer to the operations manual for the injection procedure. Upon trouble finding a suitable inguinal lymph node for injection on one side, the other side should be inspected. Only under exceptional circumstances can the injection be given into an axillary lymph node.

After the injection, the patient shall remain in the vicinity of the study site for the next hour, and the injection site will be examined by investigator/study nurse 1 hour post injection.

Study Medication: Vitamin D

Treatment with vitamin D/placebo starts at Visit 2 if the Vitamin D serum levels are below 100 nmol/L (40ng/ml) at screening. If the patient has Vitamin D serum levels above 100 nmol/L (40 ng/ml) at screening, no Vitamin D/placebo treatment will be given to that patient (the patient will only be given the Diamyd/placebo injection). Patients with vitamin D levels below 100 nmol/L (40 ng/ml) at screening will receive vitamin D/placebo administered orally (2000IE per day) for 4 months (120 days in total). The patient should be instructed to return all used and unused vitamin D/placebo bottles at Visit 6.

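### The Safety Set requires an injection although study medication starts about a month earlier, so orally dosed, never-injected patients leave every safety table; the relative-day formula for AE listings also has its sign reversed

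*Protocol*

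**What the plan says.** Protocol section 13.2.1 states that the Safety Set "will consist of all randomized patients who received at least one injection". The same section adds: "Safety presentations will be based on the safety set". The FAS is defined on a wider exposure condition, namely "all randomized patients who have received at least one dose of study medication and have at least one post-baseline assessment", together with the corresponding baseline value, for any efficacy variable.

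The regimen has two investigational products that start at different times. Section 10.1: "Treatment with vitamin D/placebo starts at Visit 2 if the Vitamin D serum levels are below 100 nmol/L". Section 10.1.3 lists vitamin D as study medication with its own IMP supplier. Visit 2 is Day 1. The first injection is at Visit 3, Day 30 (±5). Patients above the threshold receive injections only.

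Section 9.2.1 records events "as AEs from start of first administration of IMP (day of Visit 2 and onwards"). Section 13.2.3.3.1 treats events with onset at or after treatment start as treatment-emergent. Section 11.4 has causality assessed for Diamyd and for vitamin D separately.

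For AE listings, section 13.2.3.3.1 computes relative day as the date of first IMP minus the AE start date, adding 1 for events on or after first IMP.

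**The concern.** The clock for adverse events starts with the first oral dose, but entry to the safety tables needs an injection about a month later. A patient exposed only to vitamin D/placebo can have treatment-emergent events, assessed for their relation to vitamin D, that no Safety Set table shows.

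The exclusion can also depend on the safety outcome. Section 8.5 names unacceptable AEs as a reason to stop product, and section 13.2.3.3.1 calls for a row of AEs leading to discontinuation. A patient who stops for that reason during the oral-only month, before any injection, is one that row should count, and the set definition removes that patient.

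The relative-day formula is an independent error. It mis-times events in the listings.

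**Working it through.** **Who falls outside the Safety Set**

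| Patient | FAS exposure condition | Safety Set |
|---|---|---|
| Below 100 nmol/L, oral product taken, later injected | met | in |
| Below 100 nmol/L, oral product stopped early, later injected | met | in |
| Below 100 nmol/L, oral product taken, never injected | met | **out** |
| Above 100 nmol/L, injected | met | in |
| Above 100 nmol/L, never injected | not met | out |

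Only the third row is inconsistent. Injected patients keep their events from Day 1 to the first injection. The protocol's own rules can produce third-row patients:

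- Loss to follow-up before Visit 3.
- Section 10.4: a patient prescribed an excluded drug between screening and first injection is withdrawn. The part of that window after Visit 2 is relevant.
- Section 11.8: "If the pregnancy is verified prior to any of the injections, no further injection shall be given".
- Section 8.5: "Diamyd/placebo should not be given to the patient if the patient after inclusion in the study develops/experiences" a listed condition (any vaccination, head trauma and immune-suppressive treatment are examples). The same section provides for "stopping one or several investigational products, but continuing follow-up visits, including efficacy and safety evaluations".

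A patient in the last group who attends Visit 3 gives the fasting C-peptide and HbA1c samples scheduled there (section 7.1.1.5). With baseline values, that patient meets the FAS definition and is still outside the Safety Set.

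**How many**

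The protocol gives no expected number. Inputs from it: N = 106, 10% loss to follow-up (section 13.1), Month 15 = Day 450, first injection at Day 30 ± 5. Assumption, not in the protocol: losses are uniform over 450 days.

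- Expected number lost before day d = 106 × 0.10 × d/450.
- Chance of at least one = 1 − (1 − 0.10 × d/450)^106.

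| First injection at | Expected number | Chance of at least one |
|---|---|---|
| Day 25 | 0.59 | 45% |
| Day 30 | 0.71 | 51% |
| Day 35 | 0.82 | 56% |

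This table takes every patient to be below 100 nmol/L. That share is not given. At Day 30 the expected number is 0.71 × 0.90 = 0.64 if the share is 90%, and 0.71 × 0.75 = 0.53 if it is 75%. At 75% the chance of at least one is 1 − (1 − 0.10 × 30/450 × 0.75)^106 = 41%.

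If losses come early, the number rises. With 10% of all losses before the first injection it is 10.6 × 0.10 = 1.06, and with 25% it is 10.6 × 0.25 = 2.65. Sections 8.5, 10.4 and 11.8 add an amount for which no rate is given.

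**Relative day**

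Let k be the AE start date minus the date of first IMP, in days. As written, the result is −k + 1 for k ≥ 0 and −k for k < 0. The usual convention is k + 1 and k.

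| k | As written | Intended |
|---|---|---|
| −5 | 5 | −5 |
| −1 | 1 | −1 |
| 0 | 1 | 1 |
| 1 | 0 | 2 |
| 39 | −38 | 40 |
| 449 | −448 | 450 |

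Pre-treatment events get positive days, and events two or more days after first dose get negative ones. The day before first dose and the day of first dose both come out as day 1.

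**The case against.** The strongest reply is about weight. On the base-case assumptions fewer than one patient in 106 is affected. No efficacy result, power or type I error is touched, events stay in the eCRF, SAEs are still reported, and the DSMB works under its own charter and SAP. All of that stands.

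The loss calculation also does not count omitted events. A patient lost before Visit 3 has no scheduled post-baseline visit at which AEs are collected, so unless that patient is contacted again or returns at Month 15, the effect is mainly on the denominator. The routes more likely to leave recorded events out of the tables (sections 8.5, 10.4 and 11.8) have no rate, and some are narrow. This stands too: 51% is the chance of at least one such loss, not of at least one omitted event.

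There is also a rationale for an injection-based set. Diamyd is the unapproved product, section 5.2 anticipates no risks from vitamin D at this dose, and never-injected patients would dilute the denominator for Diamyd-related events. That supports keeping an injected subset. It does not support making that subset the only safety population when vitamin D/placebo is itself study medication with its own causality assessment.

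Finally, the relative-day error is a transposition that a programmer would probably notice. That is fair, and it should add no weight to the Safety Set point.

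**Conclusion.** Both points hold. The Safety Set does not match the exposure from which the protocol counts treatment-emergent events, and it is narrower than the exposure condition for the FAS with no reason given. Neither is a detail left open for the SAP: the protocol fixes both definitions, and section 13.2 says the SAP will follow its outline.

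The size is small. It is about 0.5 to 0.8 patients for losses uniform over 450 days, with 75% to 100% of patients taking the oral product, and up to about 2.7 if a quarter of losses come before the first injection. An unquantified number is added by the protocol's own rules on not injecting. The timing of losses and the share on the oral product are assumptions. The consequence is confined to the safety output, where it can remove exposed patients and AEs that led to discontinuation. The relative-day error is separate and minor: it affects listings only and changes no count. Both should be corrected, mainly because correction is so cheap.

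**What to change.** 1. Define the Safety Set as all randomised patients who received at least one dose of any study medication (vitamin D/placebo or Diamyd/placebo), analysed by treatment actually received. For patients above 100 nmol/L this gives the same set as now.
2. Add a subset with at least one injection for injection-site reactions. It can also serve for a supplementary display of Diamyd-related events, which answers the dilution point.
3. Define relative day as (AE start date − date of first IMP) + 1 for events on or after first IMP, and as (AE start date − date of first IMP) for earlier events.

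The cost is an edit to two definitions, plus the subset, before unblinding. No new data are needed and trial conduct does not change.

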13.2.2 Statistical and Analytical Plan

In general, data will be presented using summary statistics. For continuous variables number of observations, mean, standard deviation, minimum, median, and maximum will be given. Categorical variables will be presented as frequencies and percentages. For all statistical analyses, p-values and 95% confidence intervals will be given. The tabulation of the descriptive statistics will be split by treatment group and visit, as applicable.

